### 3.3 PRIMARY AND SECONDARY ENDPOINTS:

*Primary endpoint:* A patient will be deemed a success if each of the following parameters were measured:

1. Identify tumor associated vessels and measure vessel diameters
2. Determine vessel density per 10x field
3. Visualize vital dyes within the tumor-associated vessels (fluorescein)
4. Calculate the blood flow velocity of the tumor-associated vessels and tissue penetration of fluorescein as a marker of vessel permeability.

Measurements will be obtained before and after any tumor vessel manipulation with either bolus fluids or vasopressors.

*Secondary endpoints:*

1. Post-operative comparison of the microvasculature of tumor with normal tissue (e.g. peritoneum) in each individual subject using vessel diameters, vessel density, detection of intravital dye and flow rates.
2. Post-operative correlation of the microvasculature with pathologic features of the tumor (i.e. tumor grade) at the time of the final pathology report (5-7 days after surgery).
3. Post-operative correlation of the microscopic observation of the tumor microvasculature tumor-specific and overall survival.

## 4 METHODOLOGY

### 4.1 Study Design

This is an open-label, non-randomized, single center, study of IVM observation in conjunction with fluorescein in subjects with deep space solid tumors undergoing surgical resection. The first part is a Pilot study of feasibility.

Subjects will be treated on an inpatient basis. All subjects will meet the inclusion and exclusion criteria summarized in **Section 5.1** and **Section 5.2** prior to participation in this study. Standard evaluation by the Preoperative Anesthesia clinic may include additional testing such as EKG, chest x-ray, and/or pulmonary function tests, but this is performed based upon their established

guidelines. If any of these tests preclude a surgery in the operating room, then the patient is excluded from this study.

#### 4.2 STUDY METHODS

During the course of treatment for deep space solid tumors while the patient is under anesthesia, surgical resection will be performed. Approach to surgery may include open, laparoscopic, or robotic, as the HIVM microscope can be used through any of these approaches.

The IVM technology utilized at Mayo Clinic currently consists of a high resolution confocal endomicroscope (Appendix C). This apparatus has the ability to provide single cell resolution and high quality images of the microvasculature. While the typical application of this device is to investigate GI mucosal surfaces (i.e. esophagus or colon), it can be readily and easily applied to any surface. It can be sterilized via standard STERRAD techniques or used with a sterile sleeve in order to interface with the peritoneal surface, as currently used in NCT03517852: Intravital Microscopy (IVM) in Patients with Peritoneal Carcinomatosis (PC).

The microscope will be moved into position next to the OR table by the operating surgeon after the tumor is exposed. The microscope will be covered with a standard sterile drape similar to that used for cords associated with other intraoperative devices (NeoProbe or intraoperative ultrasound). The only exposed area will be the microscopic objective located at the tip of the endoscope, which will be made sterile along with the entire probe. This microscopic objective will come into close contact with the peritoneal surface for microscopic observation. Once the microscopic objective is in proper position, the epifluorescent light source will be turned on and digital video recording will commence. All video images will be captured to the hardware directly attached to the microscope (Appendix C). All data will be backed up on a password-protected hard drive in the Principal Investigator's laboratory.

1-2 mL of 10 or 25% fluorescein will be injected intravenously and observation will continue until loss of fluorescence over 2-4 areas of both grossly normal and tumor tissue. IVM is continuously performed at the time the fluorescent agent is injected and video is recorded in real-time. The fluorescein is almost immediately visible within the microscopic field, and the vessels are quickly outlined in great detail. The fluorescence lasts for a few minutes (2-3 minutes) and then either fades or begins to permeate through the tissue. The extravasation of dye will be determined by visualizing fluorescence outside of the defined vessels for a total time of 5 minutes. The distance from the vessels will be measured, recorded, and expressed as a function of time (extravasation rate) in an analysis performed off-line from the digitally recorded video. On average, the total observation time per field is 1-2 minutes.

During the course of the surgery, if fluid boluses and/or vasopressors (e.g. vasopressin and/or phenylephrine) are required and administered to maintain blood pressure during the resection, another round of IVM observations will be performed with a second dose of 1-2 mL of fluorescein. Communication with anesthesia will indicate when fluid boluses and/or vasopressors are administered, in order to coordinate the observation.

At the completion of the entire observation period, the microscope will be removed and sterilized between uses. This would complete the observation period, which is anticipated to take 10 – 12 minutes total time. The observation will take place during the course of standard surgery and is not anticipated to delay or lengthen the duration of the procedure. In fact, during this observation period, other portions of the surgical procedure will be performed, including pathologic biopsy assessment, margin assessment, intra-abdominal irrigation, drain placement and securement, implantation of hemostatic agents (Surgicel, Tissell spray, GelFoam, etc), or in the case of more than one tumor or satellite tumors, additional dissection of the remaining tumors. The patient will recover in the PACU per standard protocol. The patient will be monitored for any allergic reactions and/or side effects to fluorescein administration and treated appropriately as described in previous sections.

Technical difficulties with the microscope apparatus (e.g. malfunction of the software or structural damage to any of the microscope components) or unforeseen events during the course of surgery that are unrelated to the study intervention but that result in the termination of the surgery (e.g. adverse reaction to anesthetic prior to administration of fluorescein or hemodynamic instability from a complication of the surgery) will not be considered failures of the primary objective. In these circumstances, the subject will be considered to be off-study and be replaced with a subsequent patient. If vasopressors are not administered during the course of the surgery, the patient data will still be included in the study as it addresses Aim 1.

Off-line analysis of digitally recorded live video will be performed using parameters and statistical methods that have been developed in our preclinical imaging studies.[1] Lumenal cross-sectional diameter (D) of vessels and velocity (V) of dye labeled cells will be measured in off-line observations. Wall shear rate ( $\gamma$ ) will be calculated as  $8(V \div D)$ .[44] Vessel density will be determined by measuring the calculated blood vessel area as a percent of the total visual field area. If visible, the uptake of fluorescein will be measured as a diffusion rate (distance from tumor vessel over time) and as a percent of the total tumor field observed (percent of visual field expressed as surface area with dye detected). Blood flow velocity will be determined by the equation  $Q = (RBC \text{ velocity}/1.6) \times (d/2) \times \pi$ . Software is available from Mauna Kea, which can analyze and calculate these data.

These data will be calculated and recorded in a spread sheet that will also be saved onto a password-protected hard drive in the Principal Investigator's laboratory. Additionally, all data will be de-identified and provided to the Biostatistician. Generated data and the raw video images will be stored for review at any time to satisfy any audit of the collected data. This saved data will readily allow the determination of a successful observation including the identification of tumor vessels, the associated vessel measurements, vessel density, and dye enhanced imaging acquisition.

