### 1.1.2 CLINICAL STUDIES WITH FLUORESCEIN

This protocol intends to apply the commonly used intraoperative fluorescent agent, fluorescein, to further characterize blood vessels associated with deep space solid tumors. It is anticipated that fluorescein will be readily detectable in the microscopic field of observation following intravenous fluorescein injection.

Fluorescein is not expected to have a direct intervention on tumor biology. Fluorescein is routinely used during the course of surgery for a variety of indications (e.g. intraoperative assessment of bowel or organ perfusion, vessel angiography of the retina) and is deemed non-toxic with no long term side effects.

Clinically, fluorescein is most commonly used for ophthalmologic procedures including fluorescein angiography with intravenous injection. Fluorescein angiography is performed by injecting fluorescein sodium dye as a bolus into a peripheral vein. The normal adult dosage is 500 mg, and is typically packaged in doses of 5 mL of 10% or 2 mL of either 10 or 25% concentration. For pediatric patients, the dose is adjusted to 35 mg per 10 pounds of body weight.[17]

Upon entering the circulation, approximately 80% of the dye molecules bind to plasma proteins, which significantly reduces fluorescence because the free electrons that form this chemical bond are subsequently unavailable for excitation.[18] The remaining unbound or free fluorescein molecules fluoresce when excited with light of the appropriate wavelength. With a molecular weight of 376, fluorescein diffuses freely out of all capillaries except those of the central nervous system, including the retina.

The dye is metabolized by the kidneys and is eliminated through the urine within 24 to 36 hours of administration. During this period of metabolism and elimination, fluorescein has the potential to interfere with clinical laboratory tests that use fluorescence as a diagnostic marker.[19, 20] To avoid any false readings, it may be prudent to schedule clinical lab tests either before the angiogram, or postpone testing for 1 or 2 days to allow sufficient elimination of the dye. Side effects of intravenous fluorescein include discoloration of the urine for 24 to 36 hours and a slight yellow skin discoloration that fades within a few hours. Nursing mothers should be cautioned that fluorescein is also excreted in human milk,[21] for this reason, nursing mothers will be excluded from this study.

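### Dye left from the first injection can be scored as new leakage in the before/after permeability comparison, because the plan specifies no pre-injection reference.

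*Combined protocol and SAP*

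**What the plan says.** Section 4.2 describes the first round: "1-2 mL of 10 or 25% fluorescein will be injected intravenously and observation will continue until loss of fluorescence". On what follows, it says: "The fluorescence lasts for a few minutes (2-3 minutes) and then either fades or begins to permeate through the tissue". On leakage: "The extravasation of dye will be determined by visualizing fluorescence outside of the defined vessels for a total time of 5 minutes". If the patient then needs fluid or a vasopressor, "another round of IVM observations will be performed with a second dose of 1-2 mL of fluorescein". For this second round the section states no concentration, no minimum interval, no reference image before injection and no rule on whether the same fields are revisited.

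The off-line scoring, also in Section 4.2, has two measures of uptake. One is a diffusion rate, meaning distance from the vessel over time. The other is expressed "and as a percent of the total tumor field observed", meaning the area in which dye is detected. Neither has a background term.

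Section 1.1.2 says that "fluorescein diffuses freely out of all capillaries except those of the central nervous system" and that the dye "is eliminated through the urine within 24 to 36 hours of administration".

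The before/after comparison is part of the plan. Item 5 of the Synopsis primary objective asks for the vessel parameters after fluid or vasopressor. Section 3.3 calls for measurements before and after manipulation. Section 9 applies paired analyses like those for tumor against normal tissue, with no term for order or carry-over.

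**The concern.** The order is fixed: the post-intervention round always follows an earlier dose of the same dye. Anything the first dose leaves in the tissue is therefore confounded with the effect of fluid or vasopressor. Both uptake measures depend on where dye is seen, not on when it arrived. Followed as written, the scoring credits leftover dye to the intervention. More patients would not help, because the error is systematic.

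At stake is whether a before/after difference in permeability can be interpreted at all. A reference that was not recorded in the operating room cannot be recovered afterwards.

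**Working it through.** The documents give no sample size, SD, power or residual-dye level for this comparison, so there is no figure of theirs to reproduce. The check asks whether residual dye is plausible, and which way it would push each measure.

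**1. Interval between injections.** Section 4.2 describes an observation period "which is anticipated to take 10 – 12 minutes total time" but does not say whether this covers both rounds. If it does, and the second round needs its own 5-minute leakage window, the second injection comes at most 10 − 5 = 5 to 12 − 5 = 7 minutes after the first. If it does not, the gap depends on when fluid or vasopressor is needed and could be much longer.

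**2. How much dye could remain.** Two assumed clearance models bracket the answer.

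- Whole body, first order, fraction remaining exp(−kt), assuming 90% or 97% is gone by 24 or 36 hours. For 90% at 24 hours, k = ln(10)/24 = 0.096 per hour, which leaves 91% at 1 hour. Across the four combinations, 86–94% remains at 1 hour and 65–83% at 3 hours.
- Local tissue, fraction remaining 0.5^(t/half-life). The documents give no tissue half-life. For assumed values of 2, 10 and 60 minutes, 13%, 66% and 93% remains at 6 minutes, and about 0%, 2% and 50% at 60 minutes.

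Residual dye is therefore likely after a short gap. After a long one it could be negligible.

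**3. Direction, with true permeability unchanged.** Assumed model: signal at distance x from the vessel wall and time t is A·exp(−x/(c√t)) + b, with A = 1, c = 10, detection threshold θ = 0.2 and residual b. For uniform b the visible front lies at x = c√t · ln(A/(θ − b)). The field is a strip 100 units deep, so the front at 5 minutes is also the percent of field. Slope is (front at 5 min − front at 1 min)/4.

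| b (share of threshold) | ln(A/(θ − b)) | Front at 1 min | Front at 5 min (= % of field) | Distance ÷ 5 min | Slope |
|---|---|---|---|---|---|
| 0 | 1.609 | 16.1 | 36.0 | 7.2 | 4.97 |
| 0.05 (25%) | 1.897 | 19.0 | 42.4 | 8.5 | 5.86 |
| 0.10 (50%) | 2.303 | 23.0 | 51.5 | 10.3 | 7.12 |
| 0.15 (75%) | 2.996 | 30.0 | 67.0 | 13.4 | 9.26 |

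These residuals all lie below the threshold, so they would be invisible to the eye before the second injection. If b exceeds the threshold, the whole field counts as leakage and no front can be measured.

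A residual halo around the vessel behaves differently. With b = 0.25 out to 30 units, the front is at 30 at 1 minute and 36 at 5 minutes, so the slope falls to (36 − 30)/4 = 1.5. A sharp halo of 40 units gives slope 0 and 40% of field. Graded halos give slopes of 4.5 down to 2.7, while percent of field rises to between 41% and 67%.

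At equal dye signal, percent of field and wall-to-front distance were raised or unchanged in every case and never lowered. The slope went both ways.

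**4. Dye amount.** The first-round wording allows 1 mL × 100 mg/mL = 100 mg up to 2 mL × 250 mg/mL = 500 mg, and nothing requires the two rounds to match. With b = 0.10 and second-round signal A = 0.5, the front at 5 minutes is 10 × √5 × ln(0.5/0.10) = 36.0, which exactly cancels the upward error. With the background removed it is 10 × √5 × ln(0.5/0.2) = 20.5, a false decrease.

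**5. Effect of a reference.** Subtracting b, measured just before the second injection, returns the equal-dose rows to 36.0 and 4.97. It does not correct unequal dye amounts, which is why those need recording too.

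**The case against.** The strongest reply is that residual dye is inferred, not documented. Round one runs until fluorescence is lost, the text says the signal may simply fade, the 24 to 36 hours refers to urinary elimination and not to local retention, and re-imaging of the same field is not specified. All of this stands. It does not remove the problem: loss to the eye is not zero signal, and moving to a different field does not guarantee a dye-free background.

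Second, Section 4.2 starts recording once the objective is in place and images continuously through injection, with raw video kept for off-line analysis. Pre-injection frames may therefore already exist for the field in view. That is fair and makes the remedy cheap. The plan does not, however, say that those frames will be used, and areas visited only after injection would have none.

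Third, the cited preclinical methods or the vendor software may handle background. That cannot be judged here; the protocol simply does not describe it.

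Fourth, Aim 2 asks mainly about blood flow, and Section 9 names density and flow rate, not permeability, for its paired t test. This stands and limits the importance of the point.

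A reader might infer more: that post-intervention leakage will be overstated in every measure, more so in leakier tumors, with a calculable false-positive rate. The documents do not support that. The slope can fall, unequal dye amounts can reverse the error, nothing quantifies a link to tumor leakiness, and no SD or residual level is given from which to compute an error rate.

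**Conclusion.** The point holds in a limited form. The before/after permeability comparison can be confounded by dye from the first injection, because the second dose follows in the same operation with no stated interval and no pre-injection reference. If residual dye is present, percent of field and wall-to-front distance are biased upward, all else equal; a front-slope rate can be biased either way. The 36% to 42–67% range shows sensitivity under assumed parameters and does not estimate this trial's bias.

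The feasibility endpoint asks only whether the parameters could be measured, so it is not shown to be affected, nor are the flow, diameter and density comparisons. The change is worth making because it is cheap and the missing reference cannot be recreated after surgery.

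**What to change.** In Section 4.2:

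- Require a few seconds of video of each second-round field that will contribute to the permeability comparison, immediately before the second injection and at the same settings.
- Analyse uptake as the increase over that background, and state whether the extravasation rate is a slope or distance divided by time.
- Record the interval between injections and the amount of dye given in each round.

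In Section 9, limit the before/after permeability comparison to fields with such a reference and label it exploratory. Where there is no reference, restrict the before/after comparison to diameter, density and velocity.

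The cost is a few seconds of recording per field and one subtraction step. The main drawback is that fewer fields will contribute, since the same field must be held from the reference clip through the leakage window and several areas are otherwise visited in each round. No change to dosing or clinical care is involved.
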